14.2.1.2. Treatment Phases for Exacerbations

Treatment State	Definition
Pre-Treatment	
 Exacerbation onset date < First dose of study treatment
On-Treatment	
 First dose of study treatment ≤ exacerbation onset date ≤ First dose of study treatment + 28 days Any exacerbation with missing onset date will be assumed to be “On-Treatment”. Any exacerbation with partial onset date will be assumed to be “On-Treatment” unless there is evidence to the contrary (e.g. month/year of onset is present and is earlier than the month/year of the first dose of study treatment).
Post-Treatment	
 Exacerbation onset date > First dose of study treatment + 28 days

14.3. Appendix 3: Data Handling Conventions

14.3.1. Baseline Definition & Derivations

14.3.1.1. Baseline Definitions

- Baseline will be defined for all subjects in the ‘All Subjects (Safety)’ population.
- The baseline values for each assessment will be the latest available assessment prior to administration of mepolizumab at Visit 2.

14.3.1.2. Derivations and Handling of Missing Baseline Data

Definition	Reporting Details
Change from Baseline	= Post-Dose Visit Value – Baseline
% Change from Baseline	= 100 x [(Post-Dose Visit Value – Baseline) / Baseline]
Ratio to Baseline	= Visit Value / Baseline

NOTES :

- Unless otherwise specified, the baseline definitions specified in Section 14.3.1.1 Baseline Definitions will be used for derivations for endpoints / parameters and indicated on summaries and listings.
- Unless otherwise stated, if baseline data is missing no derivation will be performed and will be set to missing.

14.3.2. Reporting Process & Standards

Reporting Process	
Software	

 • The currently supported versions of SAS software will be used. 	
Reporting Area	
HARP Server	: uk1salx00175
HARP Area	: sb240563/mid205667
Analysis Datasets	

 • Analysis datasets will be created according to CDISC standards. • For creation of ADaM datasets (ADCM/ADAE), the same version of dictionary datasets will be implemented for conversion from SI to SDTM. 	
Generation of RTF Files	

 • RTF files (rich text format) will be generated for the final reporting effort. 	

Reporting Standards	
General	

 • The current GSK Integrated Data Standards Library (IDSL) will be applied for reporting, unless otherwise stated: 
 ○ 4.03 to 4.23: General Principles ○ 5.01 to 5.08: Principles Related to Data Listings ○ 6.01 to 6.11: Principles Related to Summary Tables ○ 7.01 to 7.13: Principles Related to Graphics 	

Reporting Standards	

 ○ Safety and study population displays will be based on the core IDSL templates for these data types. 	
Formats	

 ● The reported precision (decimal places) will follow the IDSL statistical principles but may be adjusted to a clinically interpretable number of decimal places (DPs). 	
Planned and Actual Time	

 ● Reporting for tables, figures and formal statistical analyses: 
 ● Planned time relative to dosing will be used in figures, summaries, statistical analyses and calculation of any derived parameters, unless otherwise stated. ● The impact of any major deviation from the planned assessment times and/or scheduled visit days on the analyses and interpretation of the results will be assessed as appropriate. ● Reporting for Data Listings: 
 ● Planned and actual time relative to study drug dosing will be shown in listings (Refer to IDSL Statistical Principle 5.05.1). ● Unscheduled or unplanned readings will be presented within the subject's listings. ● Visits outside the protocol defined time-windows (i.e. recorded as protocol deviations) will be included in listings. 	
Unscheduled Visits	

 ● Data recorded at an unscheduled visit will be re-assigned to the closest nominal visit at which collection of data was scheduled, unless information already exists at that visit. Unscheduled data re-assigned to a scheduled visit will be reported in summary tables and figures. Unscheduled data that is not re-assigned to a scheduled visit will not be included in summary tables or figures. ● Data from all unscheduled visits will be included in listings and individual subject figures. 	
Descriptive Summary Statistics	
Continuous Data	Refer to IDSL Statistical Principle 6.06.1
Categorical Data	N, n, frequency, %
Reporting of Pharmacokinetic Concentration Data	
Descriptive Summary Statistics	Refer to IDSL Statistical Principle 6.06.1 Assign zero to non-quantifiable (NQ) values (Refer to GUI_51487 for further details)
Graphical Displays	

 ● Refer to IDSL Statistical Principles 7.01 to 7.13. 	

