7.9. Pharmacokinetics

Blood samples for analysis of mepolizumab plasma concentration will be obtained as per the Time and Events table (Section 7.1). Samples obtained at Visits 2, 3, 4 and 5 should be drawn prior to dosing. The date and exact time of collection for each sample will be documented in the eCRF.

Details for collection and processing of samples may be found in the SRM.

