12.4. Appendix 4: Liver Safety Required Actions and Follow up Assessments

12.4.1. Liver chemistry stopping criteria and required follow up assessments

Liver Chemistry Stopping Criteria - Liver Stopping Event	
ALT-absolute	ALT \geq 8xULN
ALT Increase	ALT \geq 5xULN but <8xULN persists for \geq 2 weeks ALT \geq 3xULN but <5xULN persists for \geq 4 weeks
Bilirubin^{1,2}	ALT \geq 3xULN and bilirubin \geq 2xULN (>35% direct bilirubin)
INR²	ALT \geq 3xULN and INR>1.5, if INR measured
Cannot Monitor	ALT \geq 5xULN but <8xULN and cannot be monitored weekly for \geq 2 weeks ALT \geq 3xULN but <5xULN and cannot be monitored weekly for \geq 4 weeks
Symptomatic³	ALT \geq 3xULN associated with symptoms (new or worsening) believed to be related to liver injury or hypersensitivity
Required Actions and Follow up Assessments following ANY Liver Stopping Event	
Actions	Follow Up Assessments

 Immediately discontinue study treatment Report the event to GSK within 24 hours Complete the liver event CRF and complete an SAE data collection tool if the event also meets the criteria for an SAE² Perform liver event follow up assessments Monitor the subject until liver chemistries resolve, stabilize, or return to within baseline (see MONITORING below) Do not restart/rechallenge subject with study treatment. Permanently discontinue study treatment and may continue subject in the study for any protocol specified follow up assessments 	
 Viral hepatitis serology⁴ Only in those with underlying chronic hepatitis B at study entry (identified by positive hepatitis B surface antigen) quantitative hepatitis B DNA and hepatitis delta antibody⁵. Blood sample for pharmacokinetic (PK) analysis, obtained within 4 weeks after last dose⁶ Serum creatine phosphokinase (CPK) and lactate dehydrogenase (LDH). Fractionate bilirubin, if total bilirubin \geq 2xULN Obtain complete blood count with differential to assess eosinophilia. Note: The mechanism of action of mepolizumab leads to lowering of eosinophils.

Liver Chemistry Stopping Criteria - Liver Stopping Event	

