- c. Parasitic screening is only required in countries with high-risk or for subjects who have visited high-risk countries in the past 6 months. Sites should use local laboratories.
- d. Perform prior to mepolizumab administration during the study and prior to restarting pre-study mepolizumab treatment on study completion/early withdrawal.
- e. Subjects will be instructed to contact clinical study staff at any time if they have concerns or questions regarding self-administration. They will have the option of returning to the clinical site for further training or assistance with self-administration. Requirement for additional training or assistance will be documented.
- f. Self-administration of mepolizumab using the safety syringe should occur within 24 hours following the clinic visit.
- g. Includes measurement of eosinophil levels for pharmacodynamic analysis at Visits 2, 3, 4 and 5
- h. Pharmacogenetic sample may be drawn any time after the respective informed consent form is signed and the subject is enrolled.
- i. Vital signs include temperature, sitting blood pressure, respiratory rate and pulse.

CONFIDENTIAL

205667

- j. Any SAEs assessed as related to study participation (e.g., study treatment, protocol-mandated procedures, invasive tests, or change in existing therapy) or related to a GSK concomitant medication, will be recorded from the time a subject consents to participate in the study up to and including any follow up contact. All other AEs/SAEs are recorded from the start of study treatment until the End of Study / Early Withdrawal visit.
- k. Injection site reactions (e.g., induration, erythema, edema, rash, pruritus, pain) are to be recorded on both AE and SAE CRF forms.
- l. Information on systemic reactions and events that meet the anaphylaxis criteria is collected on both AE and SAE CRF forms.
- m. Patient diary should be dispensed prior to administration of injection
- n. For any subject who withdraws prior to Week 12, patient diary and study drug for self-administration outside of clinic will be returned at the Early Withdrawal visit (if applicable).
- o. Assessment to be completed at the Early Withdrawal visit only if the dose of mepolizumab immediately prior to withdrawal was administered outside of the clinic.
- p. Includes both the injection outside the clinic from Week 4 and the injection in clinic at Week 8
- q. In a subset of subjects only. Completed over the telephone after the End of Study/Early Withdrawal Visit

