14.4. Appendix 4: Derived and Transformed Data

14.4.1. General

Multiple Measurements at One Time Point

 May arise when unscheduled visits are re-assigned to a nominal visit (see Section 14.3.2). If there is data at the nominal visit, the nominal visit data will be used in the summary tables and figures. All assessments will be listed. Subjects having both High and Low values for Normal Ranges at any post-baseline visits for safety parameters will be counted in both the High and Low categories of “Any visit post-baseline” row of related summary tables. This will also be applicable to relevant Potential Clinical Importance summary tables.
Study Day

 Calculated as the number of days from first dose of mepolizumab at Visit 2: 
 Ref Date = Missing → Study Day = Missing Ref Date < Visit 2 Date → Study Day = Ref Date – Visit 2 Date Ref Date ≥ Visit 2 Date → Study Day = Ref Date – (Visit 2 Date) + 1

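### SAP 14.3.2 moves unscheduled samples to the closest visit without a dose-side check, so a post-dose or mid-interval value can fill an empty pre-dose row (minor)

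*SAP*

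**What the plan says.** SAP 14.3.2 (Unscheduled Visits) gives the rule: "Data recorded at an unscheduled visit will be re-assigned to the closest nominal visit at which collection of data was scheduled", with one exception, "unless information already exists at that visit". It adds that "Unscheduled data re-assigned to a scheduled visit will be reported in summary tables and figures". SAP 14.4.1 repeats the exception: "If there is data at the nominal visit, the nominal visit data will be used in the summary tables and figures". Neither section mentions dosing, a maximum distance or what to do with a tie.

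The values that these rows are meant to hold are pre-dose. Protocol 7.9 says of PK: "Samples obtained at Visits 2, 3, 4 and 5 should be drawn prior to dosing". Footnote d of the Time and Events table puts haematology (including eosinophils), PK and antibody samples before the study dose. Doses 1 and 3 are given at Visits 2 and 4. For dose 2, footnote f says: "Self-administration of mepolizumab using the safety syringe should occur within 24 hours following the clinic visit".

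PK summaries in SAP 8.1 are by nominal time. Under SAP 14.3.2, tables and figures use planned time relative to dosing, and actual time appears in listings.

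Baseline has its own rule in SAP 14.3.1.1: "The baseline values for each assessment will be the latest available assessment prior to administration of mepolizumab at Visit 2".

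**The concern.** Each of Visits 2, 3 and 4 is followed by a dose on the same day or within 24 hours. Calendar distance is therefore a poor guide to which visit an unscheduled sample represents. A sample taken a week after a dose is closest to the visit just before that dose, where the scheduled value would have been a trough. A sample taken a little past mid-interval is closest to the next visit and would be labelled a trough before the interval has run its course.

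Trough concentration at Weeks 4, 8 and 12 is a stated endpoint, and protocol 4.4 notes that it can be compared with historical data. A re-assigned value would sit in the by-visit PK tables and figures under the nominal label.

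For eosinophils, the exposed place is the absolute Week 0 row. If the Visit 2 sample is missing, baseline falls back to the screening value while the Week 0 row could be filled by a post-dose count. One subject's two pre-treatment figures would then come from opposite sides of the first dose.

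**Working it through.** The documents give no figure that depends on this rule, so there is nothing to reproduce. The check is a day count, then an illustration of size.

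**1. Which days map where.** Inputs: Visit 2 is Day 1, and visits are every 4 weeks, so PK and eosinophils are scheduled on Days 1, 29, 57 and 85 (Time and Events table). Each day goes to the visit with the smallest day difference.

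| Unscheduled sample on | Goes to | Days after that visit |
|---|---|---|
| Days 2–14 | Week 0 | 13, all post-dose |
| Days 16–42 | Week 4 | 13 (Days 30–42) |
| Days 44–70 | Week 8 | 13 (Days 58–70) |
| Days 72–85 | Week 12 | none |

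Days 15, 43 and 71 are ties. A sample within 24 hours after Visit 3 may still precede the home dose. The forward-mapped days begin at Day 16 (15 days after dose 1) and Day 44 (about 15 days after dose 2). Between Visits 2 and 5, the word closest limits the distance to 14 days, twice the protocol's ±7-day visit window.

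**2. Can the sample exist while the cell is empty?** Protocol 12.4.1 requires after a liver stopping event: "Blood sample for pharmacokinetic (PK) analysis, obtained within 4 weeks after last dose", plus a blood count with differential. One possible sequence, built from that section's own timings: raised ALT in the Visit 3 chemistry on Day 29, the home dose that day or the next, a stopping criterion met through 2 weeks' persistence (Day 43), and follow-up samples within 24 to 72 hours (Days 44–46). Those days are 11 to 13 days from Day 57 and 15 to 17 from Day 29, so the sample goes to Week 8. If the subject has stopped treatment and next attends only the Early Withdrawal visit, the Week 8 cell is empty and the sample fills it.

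**3. Size for PK.** These assumptions are not in the documents: one compartment, half-life T of 14, 21 or 28 days, absorption rate ka of 0.15, 0.3 or 0.6 per day, and a subject not on mepolizumab at entry. With ke = ln 2 / T,

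c(t) = ka/(ka − ke) × [exp(−ke·t) − exp(−ka·t)].

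Back-mapped sample, s days after the dose:
- Week 4 ratio = [c(28+s) + c(s)] / c(28)
- Week 8 ratio = [c(56+s) + c(28+s) + c(s)] / [c(56) + c(28)]

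Example, T = 21, ka = 0.3, s = 7: (0.354 + 0.754) / 0.446 = 2.49 at Week 4.

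Over all nine parameter pairs at s = 2, 7 and 13, the ratio runs from 1.39 to 3.48 at Week 4 and from 1.24 to 2.92 at Week 8. On a daily grid from 2 to 13, the upper ends are slightly higher. At T = 14, ka = 0.6, s = 4 they are (0.224 + 0.795) / 0.2725 = 3.74 and (0.056 + 0.224 + 0.795) / 0.3406 = 3.16.

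Forward-mapped sample at 15 days: c(15)/c(28) is 1.2 to 1.9 for Week 4, and [c(43) + c(15)] / [c(56) + c(28)] is 1.3 to 1.9 for Week 8.

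**4. Effect on a mean.** If the other subjects sit at the true mean, one value with ratio R among n subjects shifts it by (R − 1)/n. The PK tables split by prior use and injection site, which gives six cells. Assuming 55 subjects spread evenly, n is about 9, and the shift is (1.4 − 1)/9 = 4% to (3.5 − 1)/9 = 28%. In a subgroup of about 27, it is 1.5% to 9%. The split is not known in advance.

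**The case against.** The strongest reply is that the empty-cell condition will usually block the problem. PK and chemistry are scheduled at the same visits, so a subject whose scheduled chemistry triggers follow-up will normally have that visit's PK sample too. Repeats of an abnormal blood count follow a value that already exists. This stands against most back-mapped cases. It does not cover the forward case in step 2 of the working, where the mapped visit was never held.

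Other safeguards also stand:
- Ratio-to-baseline denominators must be pre-dose.
- Protocol 4.4 reports that the eosinophil reduction at the end of the first interval was already close to that at steady state, so Week 4 and Week 8 counts should be little affected.
- Planned median PK profiles would barely move with one outlier.
- The PK listing shows actual times.
- SAP 14.3.2 undertakes to assess major timing deviations as appropriate, though that excludes no value.
- The SAP refers to internal reporting standards that are not available here, so a safeguard there cannot be ruled out.

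Three stronger readings are tempting but unsupported:
- The back-mapped days are 3 × 13 = 39 of the 84 from Day 2 to Day 85, so a reader might infer that nearly half of re-assigned samples are wrong. That is a share of calendar days, not of samples that meet an empty cell.
- A reader might put a number on affected subjects. The documents give no basis for one.
- Antibodies are scheduled only at Weeks 0 and 12, so Days 2–42 would map to Week 0, and a reader might infer misclassified antibody status. However, the documents describe no unscheduled antibody draw, and SAP 12.1 defines the treatment-emergent subset by a pre-dose assay.

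**Conclusion.** The concern holds as a minor defect. As written, SAP 14.3.2 can place a post-dose or mid-interval concentration in the Week 4 or Week 8 trough row, and a post-dose eosinophil count in the absolute Week 0 row. The day mapping rests only on the visit schedule and on reading closest as closest in time, which the SAP does not define.

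The size of a single wrong PK value, about 1.4 to 3.5 times the true trough at Week 4 and 1.2 to 2.9 times at Week 8, rests on outside assumptions and on a new starter. The ratio would be smaller in subjects already on mepolizumab, whose troughs are higher.

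How many subjects are affected is unknown, probably few and possibly none. The primary and secondary endpoints, the ratio-to-baseline denominators and the treatment-emergent antibody subset as defined in SAP 12.1 are not affected.

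**What to change.** Add to SAP 14.3.2, for PK and eosinophils:

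- **Week 4 and Week 8:** an unscheduled sample may fill an empty cell only if it was drawn after the previous study dose, before the dose belonging to that visit, and within the visit's ±7-day window.
- **Week 12/Early Withdrawal:** it must be within the window and before any restart of pre-study mepolizumab.
- **Week 0:** only a value meeting the baseline definition in 14.3.1.1 may be used. The same applies to any Week 0 antibody result.
- **All other unscheduled samples:** listed only. Where only the sample date is known and it equals the dose date, the sample is also listed only.

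The window also removes the ties, which fall 14 days from a visit. It tolerates no more than the protocol allows for a scheduled visit. On the assumptions in the working, a sample 21 days after dose 1 is c(21)/c(28) = 1.1 to 1.4 times the Week 4 trough.

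The cost is a few sentences and one date and time comparison. Dose dates and times are already recorded (protocol 6.8.1 and 6.8.2), as are PK collection times (7.9). Protocol 7.9 requires an exact collection time only for PK, hence the same-day rule. The downside is that a few visit cells may stay empty.

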
NOTES :
 
 1. Details of Liver Chemistry Stopping Criteria and Required Actions and Follow-Up Assessments after liver stopping or monitoring event are given in Section 5.5.2 and Appendix 4. 2. Local urine testing will be standard for the protocol unless serum testing is required by local regulation or ethics committee. 				

RBC: Red blood cell; MCV: Mean corpuscular volume; MCH: Mean corpuscular haemoglobin; BUN: Blood urea nitrogen; AST: Aspartate aminotransferase; ALT: Alanine aminotransferase; FSH: Follicle stimulating hormone
				

All laboratory tests with values that are considered clinically significantly abnormal during participation in the study should be repeated until the values return to normal or baseline. If such values do not return to normal within a period judged reasonable by the investigator, the etiology should be identified and the sponsor notified.

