12.4.2. Liver chemistry increased monitoring criteria with continued therapy

Liver Chemistry Increased Monitoring Criteria – Liver Monitoring Event	
Criteria	Actions

ALT \geq5xULN and $<$8xULN and bilirubin $<$2xULN without symptoms believed to be related to liver injury or hypersensitivity, and who can be monitored weekly for 2 weeks.
 
OR
 
ALT \geq3xULN and $<$5xULN and bilirubin $<$2xULN without symptoms believed to be related to liver injury or hypersensitivity, and who can be monitored weekly for 4 weeks.
	
 • Notify the GSK medical monitor within 24 hours of learning of the abnormality to discuss subject safety. • Subject can continue study treatment • Subject must return weekly for repeat liver chemistries (ALT, AST, alkaline phosphatase, bilirubin) until they resolve, stabilise or return to within baseline • If at any time subject meets the liver chemistry stopping criteria, proceed as described above • If ALT decreases from ALT \geq5xULN and $<$8xULN to \geq3xULN but $<$5xULN, continue to monitor liver chemistries weekly. • If, after 4 weeks of monitoring, ALT $<$3xULN and bilirubin $<$2xULN, monitor subjects twice monthly until liver chemistries normalize or return to within baseline.

References

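### The 'Any visit post-baseline' rows of the laboratory shift tables leave out unscheduled results whenever the closest nominal visit is filled, so they can miss a subject whose only qualifying value came from a repeat test

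*SAP*

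**What the plan says.** **Handling of unscheduled results.** Under SAP 14.3.2 an unscheduled result is "re-assigned to the closest nominal visit at which collection of data was scheduled, unless information already exists at that visit". For what is left over, the rule is: "Unscheduled data that is not re-assigned to a scheduled visit will not be included in summary tables or figures". SAP 14.4.1 gives the same precedence: "If there is data at the nominal visit, the nominal visit data will be used in the summary tables and figures". Unscheduled data still go into listings and individual subject figures.

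**The any-visit row.** The next item of SAP 14.4.1 describes the row for "Subjects having both High and Low values for Normal Ranges at any post-baseline visits for safety parameters". Such subjects count in both the High and the Low category. The SAP extends this to the relevant PCI tables and states no exception for unscheduled results. The tables concerned are 11.39 and 11.40 (haematology) and 11.42 and 11.43 (clinical chemistry), against the normal range and the PCI criteria respectively.

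**Repeat testing.** Protocol 7.7.7 says that clinically significantly abnormal results "should be repeated until the values return to normal or baseline". Protocol 12.4.2 adds, for liver monitoring events: "Subject must return weekly for repeat liver chemistries (ALT, AST, alkaline phosphatase, bilirubin) until they resolve, stabilise or return to within baseline". Protocol 12.4.1 calls for repeat liver chemistries within 24 hours or 24 to 72 hours of a stopping event, then twice-weekly or weekly monitoring, depending on the criterion met. Scheduled post-baseline laboratory samples are 4 weeks apart (Protocol 7.1).

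**The concern.** A reader takes a row with this label as the number of subjects with a qualifying value at any time after baseline. Under the rule it covers at most three results per parameter, one for each of Weeks 4, 8 and 12. The results left out come mainly from subjects in whom the investigator has already seen something abnormal.

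Clinically significant change in haematology or chemistry is a stated safety endpoint (Protocol 3; SAP 2.2), and these rows are its natural summary. An incomplete count could also disagree with the study's own listings. Listings 32 and 33 show subjects with values of potential clinical concern, unscheduled values included, so a subject could be listed for a value that the PCI table does not count.

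**Working it through.** The plan states no figure on this point. The check applies the rule to assumed series and asks when a *subject* count changes.

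**Inputs.** Nominal post-baseline visits are Weeks 4, 8 and 12 (Protocol 7.1). The nominal value takes precedence, and an unscheduled value is used only if its closest nominal visit is empty (SAP 14.3.2, 14.4.1). The PCI limits for potassium are below 2.8 and above 6.5 mmol/L. The ALT flag for ages 13 and over is above 239 U/L together with total bilirubin above 43 (SAP 14.6.1). Planned enrolment is 55 (Protocol 9.2.1). All laboratory values below are assumed.

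**Series 1: ALT, weekly repeats after an abnormal Week 4 value.**

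| Week | 4 | 5 | 6 | 7 | 8 | 9 | 10 | 11 | 12 |
|---|---|---|---|---|---|---|---|---|---|
| ALT (U/L) | 130 | 260 | 300 | 180 | 90 | 60 | 45 | 40 | 35 |
| Tabulated | yes | no | no | no | yes | no | no | no | yes |

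Six of the nine results are left out. The tabulated maximum is 130 and the true maximum is 300. If the Week 8 sample were missing, one repeat would fill that slot (Week 7, value 180, if the earlier of two equally close samples is taken) and five would be left out.

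This series need not lose a subject count. If 130 is above the laboratory's upper limit, the subject is already High in the normal-range row. The value 300 exceeds the ALT part of the PCI flag, but the flag also needs raised bilirubin.

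**Series 2: potassium.** Week 4 is 2.9, an unscheduled repeat soon after is 6.7, Week 8 is 4.2 and Week 12 is 4.1.

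- The tabulated values are 2.9, 4.2 and 4.1. None is below 2.8 or above 6.5, so the subject has no PCI count.
- With all results used, 6.7 > 6.5 and the subject counts as PCI High.
- In the normal-range table, assuming that 2.9 is below and 6.7 above the reference range (the documents give no reference range), the subject counts as Low but not High.
- Listing 33 would show this subject, with no matching count in the chemistry PCI table.

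**When a count is lost.** It is lost when:

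1. a repeat newly crosses a PCI limit;
2. a repeat is abnormal in the opposite direction; or
3. the first abnormal value was itself unscheduled and the scheduled values are within range.

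**Size.** One subject is 1/55 = 1.8%, two are 2/55 = 3.6% and three are 3/55 = 5.5%. Nothing in the documents says which of these, or zero, to expect.

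**The case against.** The strongest reply is that this is a disclosed convention with little effect. Tables use nominal visits and listings carry all the data. When a scheduled abnormal value prompts the repeats, the subject is already in the normal-range row. Liver monitoring under Protocol 12.4.2 requires bilirubin below 2xULN, so it seldom reaches the bilirubin-dependent PCI flags. Possible Hy's Law events are reported as SAEs, and clinically significant laboratory abnormalities meet the AE definition. The reference to any post-baseline visits could also be read to include unscheduled ones, and the IDSL shift-table template is not in the documents.

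Most of this stands as a limit on size. It does not remove the gap: the explicit exclusion from summary tables governs, and nothing visible exempts the row. The listings are a partial safeguard, because the only planned laboratory listings (32 and 33) are restricted to subjects with values of potential clinical concern.

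Four stronger readings are tempting, and the documents do not support them:

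- **That most monitoring information is lost.** With 4-weekly visits, weekly testing leaves out 3 of 4 results (75%) and twice-weekly testing 7 of 8 (88%). Those fractions count results, whereas the tables count subjects.
- **That repeats are usually the most extreme values.** Nothing in the documents shows this. Repeats continue until values return to normal or baseline, so a series may well fall.
- **That a post-dose sample placed in an empty Week 0 slot would distort baseline.** SAP 14.3.1.1 takes baseline from the latest assessment before dosing at Visit 2.
- **That a liver-event PK sample would be reported as a trough.** Protocol 12.4.1 does ask for a "Blood sample for pharmacokinetic (PK) analysis, obtained within 4 weeks after last dose". Mislabelling would need both a liver event and an empty PK slot, although PK is scheduled at every treatment visit and at early withdrawal. SAP 14.3.2 also says that major timing deviations will be assessed. This is a remote case.

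**Conclusion.** The point holds in a limited form. The SAP's rule gives an incomplete count in rows labelled as covering any post-baseline visit, and those rows *may* understate the number of subjects with an abnormality. It cannot be said that they *will*. Each missed subject is 1.8% of 55, and the frequency cannot be estimated from the documents.

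The conclusion assumes that the explicit exclusion in SAP 14.3.2 applies to these rows, that scheduled samples are mostly present, and that the unseen table template does not override the rule. The study is descriptive. The primary endpoint, the baseline derivation and the by-visit rows are not in question, and PCI-level values remain visible in the listings. It is nevertheless worth correcting, because a stated rule affects safety counts and the correction is cheap.

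**What to change.** Add one sentence to SAP 14.3.2 and one to SAP 14.4.1: the 'Any visit post-baseline' rows of Tables 11.39, 11.40, 11.42 and 11.43 use every result obtained after baseline, scheduled or unscheduled, as an exception to the exclusion of unscheduled data. Keep the nominal-visit rule for the by-visit rows. A footnote on the four tables should say that the two kinds of row draw on different sets of results.

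The cost is two sentences and a minor programming change. Reported abnormality counts may be slightly higher, and an any-visit count may exceed what the by-visit rows suggest, which the footnote explains. In return, the PCI tables and Listings 32 and 33 would rest on the same results.
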